The first clinical examination the this second comparative part will be performed at studyweek 16. A diet registration will be performed the last week before the visit. A common clinical examination will be performed and blood samples for measurements of Osteocalcin, vitamin K2, the specific BTMs, sex hormones and biochemical variables will be drawn. The participants will be given new sample of cheese and calcium tablets for four weeks and a date for the next visit.

This visit performed at week 24 is the last in clinical examination in the study and equal to the initial study visit. Blood samples will be taken for measurements of Osteocalcin, BTMs, vitamin K2 and biochemical and haematological variables. Sex hormones, muscle strength, Peak VO2, DXA investigation for BMD, TBS and LM, and RMR will be measured in the same way as at day 0.

The female participants will be interviewed about their menstruation status including menarche length, cycles day and use of hormonal contraception.

1.6.4 Dietary Monitoring:

The participants will fill in their dietary intake in an application at baseline and every 8th week of the study. During the last visit an Eating Disorder Examination Questionnaire- Short, (Prenjak K, et al BMC Psychiatry 2020;20:1–7) derived from EDE-Q © Fairburn and Beglin, 2008 will be a part of the interview.

The questions will be woven into the anamnestic interview and not as a questionnaire to ensure that the participants do not suffer from disordered eating.

1.7: Main variables

The main variables in this study will be the Osteocalcin development, BTMs, RMR and BMD. Supporting variables are muscle strength, LM and Peak VO2 and gender hormones. The vitamin K2 variants MK-7, 8, 9, 9(4H), HbA1C, vitamin D, Ca^{++,} Mg⁺⁺ and urea, will be secondary variables. As safety variables, haematological- and biochemical variables and adverse events (AE) will be recorded at each visit. The participants' activity will be continuously recorded.

1.8: Sample size

With a significant level of 5%, a power of 90% and a clinically relevant difference in total osteocalcin increase of one-time SD between the two groups, at least 24 XCSs in each group must be included. By correcting for dropouts during the first part of the study, 30 XCS will be included in each group. Totally 60 XCSs will be recruited for participation.

1.9: Study duration

The duration of the study will be 24 weeks for each participant.

Recruitment period of XCS	01.01-31.05.23

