3.2.2: Exclusion criteria.

Active XCS fulfils at least one of the following criteria will be excluded from participation in the study:

- Eating disorder
- Pregnancy
- Known gastrointestinal disorder.
- Abnormal liver or kidney function.
- Diabetes
- Suffering from verified cancer.
- Under systemic treatment with corticosteroids or other immunosuppressive drugs the last 3 weeks before start of the trial treatment.
- Participating in another clinical trial with pharmaceuticals the last six weeks before start of this trial treatment.
- Known milk product allergy.
- Suffering from diseases or injuries that disable them to perform VO2 or muscular strength tests.
- Not able to understand information.
- Do not want or not able to give written consent to participate in the study.

3.3: Recruitment of athletes

The active XCS will be recruited by the primary investigators team and by advertising in social media. They will be recruited from high schools of sports, and cross-country teams and clubs in the area around Oslo. Active XCS fulfils the inclusion and avoid the exclusion criteria will be asked to participate and to give written consent for participation.

IV: Design and randomization

4.1: Study design

The study is performed as an open randomized stratified parallel group design with two strata²⁸. Sex is used as a stratification factor. The two equal sized strata are chosen because of different Optimal Effective Dose (OED) of cheese for women and men, and because the dose-response study previously performed has shown different response in men and women²⁹.

Within each stratum the participants will be allocated into two treatment groups by block randomisation.

4.2: Randomization

The athletes will be randomized (1:1) to either daily intake of Jarlsberg cheese or Norvegia cheese by using block randomization with random block size between 2 and 6^{29} . The daily amount of cheese will be equal in the two cheese-groups with 5 slices (75g) for females and 6 slices (90g) for males.

14.3: Power Analysis

With a significant level of 5%, a power of 90% and a clinically relevant difference in total osteocalcin increase of one-time SD between the two groups, at least 24 XCSs in each group must be included. By correcting for dropouts during the first part of the study, 30 XCS will be included in each group. Totally 60 XCSs will be recruited for participation²⁹.

4.4: Identification of subjects

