All the XCS will be given one study identification number of four digits constructed as
follows:Digit 1:Indicate the gender study arm (1=female, 2=male)Digit 2&3:Indicate the athlete number consecutively within each sex arm
(01,02,03 etc.)

V: Evaluation

5.1: Osteocalcin and vitamin K

The main response variable in both the first part of the two sex arms in the study will be tOC, the bone specific markers procollagen (PINP), Collagen (CTX1), Bone specific Alkaline Phosphatase (BALP) and parathyroid hormone (PTH). In the second part of the study, Bone mineral density (BMD) will be the most central variable in addition to Resting metabolic rate (RMR), Muscle strength and peak VO₂. The Osteocalcin ratio R_0 , vitamin K_2 including the different vitamers MK 7, 8, 9 and 9/4H and vitamin K_1 will be used as secondary variables in both study parts.

5.2: Bone specific markers

The bone specific markers investigated in the study are Procollagen (PINP), Collagen (CTX1), Bone specific Alkaline Phosphatase (BALP), Parathyroid hormone (PTH).

5.3: Bone mineral density (BMD)

Participants will be weighed in their underwear, and height will be measured with a fixed stadiometer (Seca scale, Mod: 8777021094, S/N: 587728124885, Seca Deutschland, Hamburg, Germany). A dual energy X-ray absorptiometry (Lunar iDXA, E'CORE Software, version 14.10.022; GE Healthcare, Madison, WI) performing a three-site scan (lumbar area [L2-L4]; femoral neck, trochanter, and shaft [proximal femur]; and whole body compares the bone density with the bone density expected for a healthy adult of the same age, sex and ethnicity as the patient. Total body composition for different necessary measures will be performed. The difference is calculated as a standard deviation (SD) score. The difference between the patient measurement and that of a young healthy adult is known as a T score. The T scores classify as follows:

- above -1 SD is normal.
- between -1 and -2.5 SD is defined as mildly reduced bone mineral density (BMD) compared with peak bone mass (PBM)
- below -2.5 SD is defined as $osteoporosis^{30}$.

The difference between the participants measurement and that of someone of the same age and gender is known as a Z score. A Z-score below -2 indicate a bone density lower than it should be for someone of the participant's age. A Z-score is supposed to be 0, above 0 is very good, below -1 is poor. Z-Score < -1 is recommended further follow-up and clinical examination of secondary risk factors³¹.

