11.2 Statistical methods

The differences between the groups will be considered significant if the p-value is less or equal to 5 %. Comparison between groups regarding assumed continuously distributed variables will be performed by using analyses of covariance (ANCOVA) with a basic observation as covariance and repeated measurements ³⁹. Contingency table analyses will be used for comparison of discrete distributed variables.³⁸. Correlation and regression analysis will be performed to estimate the connection in the development between variables.

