11.3 Power analysis and sample size determination

With a significant level of 5%, a power of 90% and a clinically relevant difference in total osteocalcin increase of one-time SD between the two groups, at least 24 XCSs in each group must be included. By correcting for dropouts during the first part of the study, 30 XCS will be included in each group. Totally 60 XCSs will be recruited for participation²⁹.

XII: Operational Matter

12.1: Investigator's agreement

Before the start of the trial the investigator will confirm the agreement to participate in the trial by signing the Investigator's Agreement Form (Appendix IX).

12.2: Instructions

The investigators will give instructions by the data manager group and the clinical monitor supported by the project manager at the start-up visit and during the study.

12.3: Amendments to the protocol

Changes in the protocol can be required by the Ethical Committee, project manager or TINE. Changes must be written in amendments approved by the steering committee, investigator, Tina SA, and Ethical Committee. Amendments must be numbered and be together with the original protocol.

It is forbidden to add new parameters consisting of measurements on the patients in the study unless they are covered as amendments in the protocol or taken due to the health and safety of the patient.

12.4: Protocol deviations

Deviations from the protocol should be restricted as much as possible and will be fully recorded and justified. The Project manager will be informed as soon as possible of all protocol deviations.

12.5: Compliance monitoring

The Project manager and the Investigator will ensure that the site is suitable for the trial and that the participating XCS is well informed of the particulars of the trial. The Project manager and Investigators should check, protocol compliance, handling of the test articles and recording of data during the critical stages of the trial. A report is prepared of each visit and kept in the trial master file (TMF).

12.6: Responsibilities

The investigator will acknowledge the responsibilities and the agreement to participate in the trial by dating and signing the agreement form. The Project manager will verify that adequate arrangements have been made for the observations, measurements and recording of the data.

12.7: Confidentiality

The obtained data and results will be used by TINE for marketing purpose. The main study database will be stored in the product database of TINE.

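### The protocol gives two conflicting lists of main variables and names no single primary variable, yet it applies p ≤ 5% to all group differences and powers only total osteocalcin

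*Protocol*

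**What the plan says.** Two current sections rank the outcomes.

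- **Section 1.7:** "The main variables in this study will be the Osteocalcin development, BTMs, RMR and BMD". It adds: "Supporting variables are muscle strength, LM and Peak VO2 and gender hormones".
- **Section 5.1, part 1:** "The main response variable in both the first part of the two sex arms in the study will be tOC, the bone specific markers". The markers listed are PINP, CTX1, BALP and PTH, so five variables share the label.
- **Section 5.1, part 2:** "Bone mineral density (BMD) will be the most central variable in addition to Resting metabolic rate (RMR), Muscle strength", with peak VO2 closing the list.

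Section 11.2 sets one rule for all of them: "The differences between the groups will be considered significant if the p-value is less or equal to 5" per cent. The method for continuous variables is "analyses of covariance (ANCOVA) with a basic observation as covariance and repeated measurements". The section names no primary variable, order of testing or time point.

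The sample size is stated three times: in 1.8, in the power paragraph of section IV (numbered 14.3) and in 11.3. Each rests on "a clinically relevant difference in total osteocalcin increase of one-time SD between the two groups", and none says at which visit.

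**The concern.** Muscle strength and peak VO2 are supporting in one section and stand beside the most central part-2 variable in the other. RMR and BMD are main variables of the whole study in 1.7, but belong only to part 2 in 5.1. Total osteocalcin, the only variable with a power calculation, is level with four bone markers in 5.1, and with the markers, RMR and BMD in 1.7.

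Followed as written, section 11.2 lets a difference at p ≤ 5% on any one of these variables be reported as a significant main result. Because the lists disagree, strength and peak VO2 can be counted as main or as supporting after the results are known. This matters more here because the trial is open, section 8.1 ties BMD, strength and peak VO2 to a possible recommendation of the cheese, and section 12.7 says the results will be used for marketing. The stated 90% power covers none of the variables other than tOC.

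**Working it through.** **1. The protocol's own sample size.** Inputs from 11.3: 5% level, 90% power, difference of 1 SD. Two-sided testing is assumed, since the text does not say.

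- Normal approximation: n per group = 2 × (1.960 + 1.282)² / 1² = 21.0, rounded up to 22.
- Exact two-sample t-test: 23 per group.
- Stated: 24 per group, where the t-test has 92.4% power. A one-sided test would need only 18, so the figure fits two-sided testing.
- Drop-out: 24 / 30 = 0.80, an implied 20% loss.

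The sample size is therefore sound for one test of one variable, tOC.

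**2. Counting the main variables.** One test per variable.

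| List | Variables | k |
|---|---|---|
| 5.1, part 1 | tOC, PINP, CTX1, BALP, PTH | 5 |
| 5.1, part 2 | BMD, RMR, muscle strength, peak VO2 | 4 |
| 1.7 | osteocalcin (once), four bone turnover markers (listed in 5.7.3), RMR, BMD | 7 |
| 5.1, both parts pooled | all of the above 5.1 variables | 9 |

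Repeat visits are not counted, because 11.2 specifies a repeated-measures analysis and the flow chart in 1.10 gives BMD, RMR, strength and peak VO2 a single post-baseline visit at week 24. Several DXA sites (5.3) and two 1RM tests (5.4) could raise k.

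**3. Chance of at least one false positive when every null is true.** For independent tests at 5% each this is 1 − 0.95^k:

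- k = 4: 1 − 0.8145 = 18.5%
- k = 5: 1 − 0.7738 = 22.6%
- k = 7: 1 − 0.6983 = 30.2%
- k = 9: 1 − 0.6302 = 37.0%

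The protocol gives no correlations between outcomes, so a range is needed. For k two-sided normal tests with common correlation ρ, the chance is 1 − ∫ φ(u) [Φ((1.96 − √ρ u)/√(1−ρ)) − Φ((−1.96 − √ρ u)/√(1−ρ))]^k du, integrated numerically:

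| Assumed ρ | k = 4 | k = 5 | k = 7 | k = 9 |
|---|---|---|---|---|
| 0 | 18.5% | 22.6% | 30.2% | 37.0% |
| 0.3 | 17.4% | 20.9% | 27.1% | 32.6% |
| 0.5 | 15.6% | 18.3% | 23.0% | 26.9% |
| 0.8 | 11.4% | 12.7% | 14.9% | 16.6% |

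**4. Power under two repairs.** Two-sample t-test, 24 per group, 1 SD difference, two-sided:

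- Full 5% kept for tOC: 92.4%.
- 5% split equally over the seven variables of 1.7 (0.05 / 7 = 0.0071): 73.8%.

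**The case against.** The strongest reply is that tOC can be recognised as the lead variable. It alone carries the sample size, osteocalcin comes first in aim 1, in 1.7 and in 5.1, and 5.1 speaks of one main response variable. For part 2, 5.1 does put BMD ahead of the rest. On this reading a hierarchy exists but is badly written. That is fair as to intent, but it does not settle the text: the same sentence of 5.1 adds four markers on equal terms, and a primary variable inferred from a sample-size sentence has not been fixed.

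A second reply is that 11.2 only sets a general significance level, and that a multiplicity procedure or test order may stand in a statistical analysis plan that is not shown. The absence of such a procedure is indeed not counted here. What remains is a conflict between two sections of the protocol, which an analysis plan should not have to resolve.

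Third, the nine-variable figure pools two parts that 5.1 keeps apart, and 5.1 does not use the word main for the part-2 variables. That stands. The figures for five and seven variables are closest to the wording, and 37.0% should be read only as the pooled case.

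Fourth, a repeated-measures group effect could serve as the single comparison without one chosen visit. It could, but the protocol would have to say so. It does not, and tOC is measured after baseline at weeks 4, 8, 16 and 24.

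**Conclusion.** The point holds. Sections 1.7 and 5.1 contradict each other on which variables are main, no primary variable or time point is fixed, and the 5% rule in 11.2 covers all of them. For the lists as the protocol words them, the chance of at least one false-positive main result is 22.6% (five variables) to 30.2% (seven) if tests are independent, and still 12.7% to 14.9% at a correlation of 0.8, against a nominal 5%. These figures assume that all nulls are true, one two-sided test per variable, four bone turnover markers and illustrative equal correlations. The sample size itself is not wrong: it is adequate for tOC, and only for tOC. This should be changed, and wording is enough to do it.

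**What to change.** - Make the rankings in 1.7 and 5.1 identical.
- Name the Jarlsberg minus Norvegia difference in change of tOC as the single primary comparison, at two-sided 5% and one stated time point. Section 11.3 gives none. Week 8, the end of part 1, fits 5.1 and the drop-out sentence: "By correcting for dropouts during the first part of the study, 30 XCS will be included in each group".
- Label all other variables secondary, with BMD at week 24 as the leading part-2 variable. Report them with confidence intervals and make no confirmatory claim on them unless a multiplicity procedure is specified in advance.
- In 11.2, tie the confirmatory reading of p ≤ 5% to the primary comparison.

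The cost is protocol wording, which under 12.3 means a written, approved amendment. The sample size stays at 24 per group, 30 with drop-out. The drawback is that BMD, RMR, strength, peak VO2 and the bone markers cannot on their own support a confirmatory claim. In return tOC keeps its 92.4% power, rather than the 73.8% it would have under an equal seven-way split. If a claim on BMD is wanted, a fixed sequence that starts with tOC would also leave the full 5% for tOC, provided it is written down beforehand.

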5.6. Resting metabolic rate (RMR)

RMR will be measured by IC using a respiratory gas analyser (Oxycon Pro, Jaeger, Germany). Ambient conditions are registered, and the analyser is gas and volume calibrated each morning prior to the measurements, according to the recommendations stated in the user manual from the manufacturer user manual for Oxygen Pro, Jaeger, Germany. Gas exchange and ventilator variables will be measured continuously using the breath-by-breath method. Participants will be instructed to rest for 10 min, wearing a two-way breathing mask covering their nose and mouth (2700 series: Hans Rudolph, Inc). Thereafter, the measurement period is started by connecting the mask to the gas analyser, and data collection continues for a total of

20 minutes. To get reliable results a steady state of 5 minutes of no more than 10% variation of gas exchange is required. The results from the RMR measurements will be related to the estimated RMR. The most reliable formula for estimating the RMR is the Cunningham formula; 22 x Fat free mass + 500. We will obtain the fat-free mass from the DXA scan. Ratio: measured/estimated RMR should be above $0.9^{.36}$

5.7: Laboratory variables

The haematological and clinical biochemical variables to be measured are listed below.

5.7.1 Biochemical variables:

Creatinine Albumin Urea ALAT Calcium Magnesium Phosphate Ferritin Vitamin D

5.7.2 Lipids:

Total Cholesterol HDL cholesterol LDL cholesterol Triglycerides

5.7.3 Bone Turnover markers

Collagen 1 (CTX-1) Procollagen 1 (PINP) Parathyroid hormone (PTH) Bone specific alkaline phosphatase (BALP)

5.7.4 Sex hormones:

Estradiol Progesterone Testosterone LH FSH

5.7.5: Haematology

Haemoglobin (Hgb) HbA₁C

5.8: Diet registration

Diet registration will be performed by the participants. The daily intake of all food will be recorded daily for four days consecutively at screening and every eight weeks during the study. A pre-evaluated questionnaire based "diet.no" will be used and recorded on an electronical diet APP by the participants. The diet registration will be supervised by a qualified monitor. The results will be evaluated by the investigating team.

5.9: Menstruation status

To control the hormone blood sample results to female XCS, this group will be interviewed about their menstruation status. This includes menarche length, cycles day and use of hormonal contraceptives.

5.10: Cheese, supplement, and activity registration

The cheese, supplement of vitamin D and activity will med recorded in a form for daily registration. The activity will be recorded weekly. The parameters to be recorded are low- and high intensity running and roller-ski in hours, and low- and high-load strength exercise. The forms are handed out every fourth week of the study and collected by the investigator or the research assistant.

5.11: Compliance

The participants must eat their daily prescribed dose of cheese and vitamin D, register their activity weekly, and fill in their diet APP 4 days before their control every 8 weeks.

5.12: Adverse Events (AE)

5.12.1: Common Terminology Criteria for Adverse Events version 4.0 (CTCAE)

The CTCAE is divided in 26 System Organ Class (SOC) in accordance with the MedDRA hierarch. Within each SOC, AE are listed and accompanied by descriptions of severity or grade:

- Blood and lymphatic system disorders (11 Items)
- Cardiac disorders (36 Items)
- Congenital, familial, and genetic disorders (1 Items)
- Ear and labyrinth disorders (9 Items)
- Endocrine disorders (11 Items)
- Eye disorders (25 Items)
- Gastrointestinal disorders (117 Items)
- General disorders and administration site conditions (24 Items)
- Hepatobiliary disorder (16 Items)
- Immune system disorders (6 Items)
- Infections and infestations (76 Items)
- Injury, poisoning and procedural complications (78 Items)
- Investigations (38 Items)
- Metabolism and nutrition disorders (24 Items)
- Musculoskeletal and connective disorders (41 Items)
- Neoplasms benign, malignant and unspecified incl. cysts and polyps (5 Items)
- Nervous system disorders (63 Items)
- Pregnancy, puerperium and perinatal conditions (5 Items)

- Psychiatric disorders (20 Items)
- Renal and urinary disorders (20 Items)
- Reproductive system and breast disorders (51 Items)
- Respiratory, thoracic and mediastinal disorders (59 Items)
- Skin and subcutaneous tissue disorders (34 Items)
- Social circumstances (2 Items)
- Surgical and medical procedures (1 Item)
- Vascular disorders (17 Items)

5.12.2: Grading and classification

Grade refers to the severity of the AE. The CTCAE displays Grade 1 through 5 with unique clinical descriptions of severity for each AE based on this general guideline:

Grade 0 =	None
Grade 1 =	Mild: asymptomatic or mild symptoms; clinical or diagnostic.
	Observations only; intervention not indicated.
Grade 2 =	moderate: minimal, local, or non-invasive intervention indicated;
	Limiting age-appropriate instrumental Activity of Daily Living (ADL)
Grade 3 =	severe or medically significant but not immediately life-threatening:
	Hospitalization or prolongation of hospitalization indicated; disabling;
	Limiting self-care ADL
Grade 4 =	Life-threatening consequences; urgent intervention indicated
Grade 5 =	Death related to AE.

Relation to trial medication as: Definitely, Probably, Possibly or UnrelatedAction taken as:None, Interruption, Modified or DiscontinuedAE treatment as:None, Continue Medication, Procedure or Hospitalization.Outcome at last visit as:Resolved, Ongoing or Fatal.

Definitions of relationship to study treatment are as follows:

ted
or
or
te c

5.12.3: Reporting adverse events.

An adverse event (AE) is any untoward symptom or sign befalling a patient in a clinical trial regardless of its relationship to the study medications. All AEs must be described in detail and their severity and putative relationship to the study medication noted. AEs may be considered serious. The definition of this is as follows:

- Death
- Life threatening
- Leads to or prolongs hospitalization

- Results in persistent of significant disability
- Any new important medical information.

5.13 Patient factors, Vital signs, and Physical examination.

The patient factors to be recorded in the study will be age in years from birth to the screening visit, height in cm and body weight in kg. Previous medical history, duration of any disease in months from the final diagnosis to the screening visit, previous and on-going treatment of the disease will be observed. During each physical examination, body weight, concomitant disease and treatment will be recorded. Additionally, vital signs defined as Systolic and Diastolic blood pressure in mmHg and Heart rate in beats/min will be recorded in sitting position after five-minute rest. To eliminate any vitamin D disturbances the participants are provided supplement of 40μ g Vitamin D from the start till the end of the study.

VI: Study procedure

6.1: Definitions

Important definitions are:

- 1) Osteocalcin Ratio (R₀): cOC (carboxylated Osteocalcin)/ uOC (undercarboxylated osteocalcin).
- 2) Bone Mineral Density (BMD) and Trabecular Bone Score (TBS).
- 3) Lean Body Mass (LM) extracted from the body composition outcomes obtained from DXA.
- 4) RMR ratio (resting metabolic rate ratio). Observed RMR/ 22x FFM+ 500 (The Cunningham formula)
- 5) Peak VO2 which is maximal oxygen uptake.

